## 11.2 Determination of Sample Size

A power analysis was performed using the G\*Power App (Düsseldorf, North Rhine-Westphalia, DEU), where a minimum number of 28 subjects was deemed necessary to ensure the statistical power (0.95) to detect a parameter difference at the 5% significance level. The figure below shows the G-Power calculation that was used to determine the sample size.

*Figure 4: Sample Size Calculation*

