Intervention:	
The Game Ready GR PRO 2.1 is a certified product that complies with European regulations, directives and standards.
 
The system can administer ice-free cold treatment and intermittent pneumatic compression treatment, providing healthcare professionals with options for different patients, procedures, injuries and rehabilitation stages.
 
The following intervention is performed according to the manufacturer's protocol for patients with primary total knee arthroplasty: 48 hours after the operation starts the Game Ready Intervention, if tolerable, with little compression (level 1 = 5-15 mmHg) and cooling at the coldest level tolerable by the participant (corresponds to program 2). The cooling should be perceived as "pleasant" by the participant. The intervention lasts one hour, of which 30 minutes are on and 30 minutes off cycles. The on cycle includes the duration of the intervention (cooling and compression), while the off cycles include the rest period. After 60 minutes, the device is removed. If compression is not tolerated, it can also be omitted (corresponds to program 1). The intervention is performed twice a day for the first four days after surgery. The coldest tolerable temperature level is determined anew with each treatment. The compression level can be increased depending on the participant. Medium compression may only be applied from the second day onwards (corresponds to programme 3).

Control intervention (if applicable):	
In order to obtain high-quality study results, the test subjects are exposed to only one experimental condition at a time. There are two groups. In order to maintain the quality of the study, a randomized controlled trial design will be chosen. The division into the groups is randomized. The data collected in this way is pooled by outcome or group.
 
The control group will receive ordinary physiotherapy treatment, without Game Ready application.

Number of subjects with rationale:	
n=28 (14 per group) G-Power analysis: effect size at 0.8

Duration of the investigation:	
May 2022 – December 2024

Investigation schedule:	
May 2022- subject –In (planned) June 2023- subject –Out (planned)

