Investigator(s):	
Examiner:          [name] 1,2,3          [name] 1,2,3          [name] 2          [name] 2          [name] 2          [name] 2          1 University College Physiotherapy Thim van der Laan, [name]          2 University of Applied Sciences and Arts Southern Switzerland, Rehabilitation and Exercise Science Laboratory (RESlab), Department of Business Economics, Health and Social Care, Physiotherapy Graubünden, [name]          3 Vrije Universiteit Brussels, Faculty of Physical Education and Physical Therapy, [name]
 
Contact / Principal Investigator:          [name]          University of Applied Sciences and Arts Southern Switzerland          Physiotherapy Graubünden          [name] [name] [name]          [contact]

Investigational Site(s):	
Single-centric investigation:          Regionalspital Surselva AG          [name]          [name]

Statistical considerations:	
Repeated measure ANOVA          Two-way          Bonferroni correction          Factors:          -Task          -Time          The significance level is set at <math>p<0.05</math>, and the statistical data analysis is carried out with SPSS.

Compliance statement:	
This investigation will be conducted in compliance with the CIP, the current version of the Declaration of Helsinki, ISO14155, ICH-GCP (as far as applicable) as well as all national legal and regulatory requirements.

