## 5. CLINICAL INVESTIGATION OUTCOMES

### 5.1 Primary Outcome

This study aims to investigate the effects of cryotherapy with intermittent dynamic compression with Game Ready during a hospital stay. The preoperative measurement is the baseline, the 4th postoperative day is the primary endpoint and the measurement 6 weeks postoperative is declared as follow-up. The following parameters are examined for this purpose:

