## 6. CLINICAL INVESTIGATION DESIGN

### 6.1 General clinical investigation design and justification of design

Randomized, controlled trial

It is a clinical investigation concerning medical devices (MD), Category according to Art 6 ClinO-MD (A1), whereby a CE-certified medical device is tested in the intervention group.

The group size of the participants is n=28 people (per group n=14 people). The group assignment is randomized.

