## 11.3 Statistical criteria of termination of the investigation

Only data from subjects who have completed the entire protocol will be included in the study. This ensures that all data has been collected under the same conditions and thus remains homogeneous and comparable.

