## 11.4 Planned Analyses

### 11.4.1 Datasets to be analysed, analysis populations

Only complete data sets will be included in the study. Data that contains only part of the protocol is not included in the analysis. No new subjects are being sought to replace the missing data.

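### Enrolment equals the stated minimum of 28 with no numerical inflation for loss, the completers-only rule drops patients who have Day-4 data but miss week 6, and the rules for losses conflict

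*Combined protocol and SAP*

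**What the plan says.** **Sample size.** Section 11.2 states that "a minimum number of 28 subjects was deemed necessary to ensure the statistical power (0.95" for a difference at the 5% significance level. It refers to Figure 4 for the calculation. The synopsis gives "n=28 (14 per group) G-Power analysis: effect size at 0.8". Section 6.1 makes the same number the full enrolment: "The group size of the participants is n=28 people (per group n=14 people". No loss rate or inflation appears anywhere.

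**Time points.** Section 5.1 says "the 4th postoperative day is the primary endpoint", with the preoperative measurement as baseline and six weeks as follow-up. Section 11.4.2 plans a repeated-measures analysis with two groups and three times, at p < 0.05.

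**Who is analysed.** Section 11.3: "Only data from subjects who have completed the entire protocol will be included in the study". Section 11.4.1: "Data that contains only part of the protocol is not included in the analysis". Section 11.5 keeps the data of a patient who does not finish, but leaves them out of the final analysis.

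**Losses.** Section 11.4.1: "No new subjects are being sought to replace the missing data". Section 7.4 says that after a withdrawal the patient's lot goes back into the draw and another participant is recruited. It also says that data gathered before consent is revoked have to be evaluated.

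**The concern.** Two features combine. The enrolment is exactly the number that the calculation calls a minimum, so each patient who is lost and not replaced takes the analysed number below it. The completers-only rule then creates losses that need not occur: a patient can supply baseline and the primary time point in full and still be discarded for missing a follow-up visit.

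The larger stake is bias. Whether a patient returns at six weeks may depend on recovery, pain or satisfaction with the treatment. Dropping non-returners from the Day-4 comparison means that the groups compared are no longer the groups randomised. Replacing patients would restore the count but not remove this selection.

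The conflicting rules matter in practice. Site staff cannot tell whether to recruit a replacement, and the statistician cannot tell whether to include data from a patient who has withdrawn consent.

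**Working it through.** **1. Reproducing 28.** The inputs are power 0.95 and alpha 0.05 (11.2), effect size 0.8 (synopsis), and two groups and three times (11.4.2). The text does not give the scale of the effect size. Of the variants tried, the one that returns exactly 28 is the group-by-time interaction of a repeated-measures MANOVA with f(V) = 0.8:

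- λ = f² × N, df1 = (2 − 1)(3 − 1) = 2, df2 = N − 3; power = P(noncentral F > 5% critical value).
- N = 28: λ = 0.64 × 28 = 17.92, df2 = 25, critical F = 3.385, power 0.955.
- N = 27: λ = 0.64 × 27 = 17.28, df2 = 24, critical F = 3.403, power 0.947.

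The smallest N reaching 0.95 is therefore 28, as 11.2 states, and nothing has been miscalculated. With the alternative convention λ = f² × (N − 2), the minimum is 30 and power at 28 is 0.940.

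**2. Power if completers fall below 28** (same test, alpha 0.05, no replacement):

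| Completers | Lost of 28 | Power |
|---|---|---|
| 28 | 0 | 0.955 |
| 27 | 1 (3.6%) | 0.947 |
| 26 | 2 (7.1%) | 0.937 |
| 24 | 4 (14.3%) | 0.913 |
| 22 | 6 (21.4%) | 0.882 |

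The loss levels are assumptions. If patients are lost independently, the chance that all 28 complete is 0.95^28 = 0.24 at 5% loss and 0.90^28 = 0.05 at 10%.

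**3. How much of that is avoidable.** This is a simulation of the same interaction test with 14 per group, correlation 0.5 between visits, a true effect at Day 4 only with f(V) = 0.8, and the six-week visit missing completely at random and equally in both arms. These settings are assumptions. With 4 of 28 missing week 6, power is about 0.945 on all available visits against 0.91 on completers. With 6 missing, it is 0.94 against 0.88. Most of the loss is recovered, but these figures do not give the power of a Day-4 contrast.

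**4. The rules for losses side by side.**

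| Question | Section 7.4 | Section 11 |
|---|---|---|
| Is a lost patient replaced? | Yes, after withdrawal | No (11.4.1) |
| Are data already collected analysed? | Yes, after consent is revoked | No, if the protocol is incomplete (11.3, 11.4.1, 11.5) |

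On the first row, 7.4 may be meant for withdrawals and 11.4.1 for incomplete records, but the text does not say so. On either reading, a patient who stays in the study but misses the six-week visit is dropped and not replaced. On the second row, a patient who revokes consent before finishing falls under both rules, and they give opposite answers.

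**The case against.** **The power cost is small.** This stands. One loss costs under one point, and four still leave power above 0.90. No loss rate is documented, and the participant payment follows the six-week measurements (9.3.2), which should help retention. The case for change rests more on selection bias and wasted data than on power.

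**Four stronger readings are tempting, and the documents do not support them.**

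- A reader might infer that the plan makes no provision for loss at all. Section 7.4 does provide for replacing withdrawals. What is missing is a numerical inflation and a consistent rule.
- A reader might infer from "Bonferroni correction" in the synopsis that the 0.95 fails once alpha is divided over all ten listed outcomes. The family is not defined, and post-hoc pairwise comparisons are an equally natural reading. Some outcomes cannot have a three-visit group-by-time test: satisfaction is asked only of the device group, length of stay is a single value, and morphine is a daily count.
- A reader might take 0.8 as a difference of 0.8 SD and call the trial underpowered. The text does not give the scale, Figure 4 is not available here, and 28 reproduces under f(V).
- A reader might conclude that a reserve should be enrolled. For an assumed 10% loss, 28 / 0.9 = 31.1, which exceeds the limit in 10.3, where the study is described as having 30 or fewer subjects.

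**Conclusion.** The point holds as a matter of analysis population and inconsistent rules, not as an error in the sample-size arithmetic. The contradiction between a Day-4 primary endpoint and exclusion for missing week 6 follows from the text alone, as do the conflicts between 7.4 and section 11. No assumption is needed for these.

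The power figures (0.955 at 28 completers, 0.947 at 27, 0.913 at 24, 0.882 at 22) are conditional on f(V) = 0.8, the interaction test, λ = f² × N and alpha 0.05. They show a modest cost for a few losses. The size of any selection bias cannot be estimated from the documents. The point should be fixed, because the remedy is cheap and protects the primary comparison. Confidence is medium, because the scale of the effect size is inferred and the loss rates are assumed.

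**What to change.** 1. **Sections 11.3, 11.4.1 and 11.5.** Replace the completers-only rule. Analyse all randomised patients in their assigned group using all available visits, for example with a mixed model containing group, time and group-by-time and with Day 4 as the primary time point. Keep the completers analysis as a sensitivity analysis.
2. **Section 7.4 against section 11.** Reconcile 7.4 with 11.4.1 on whether, and in which cases, a patient is replaced. Reconcile 7.4 with 11.3, 11.4.1 and 11.5 on whether data already collected from withdrawn patients are analysed.
3. **Section 11.2.** Say that the 0.95 applies to 28 analysed patients at alpha 0.05. Restate the power for the test and alpha that the primary analysis will actually use; the completers' interaction figures above should not be carried over to a Day-4 contrast.

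**Cost.** The change needs rewording and slightly more analysis work, with no extra visits or patients. The mixed model relies on a missing-at-random assumption, and it does not recover patients lost before Day 4. Changing the analysis population may count as a substantial amendment and need ethics committee approval (2.9, 2.10).

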## **11. STATISTICAL METHODS**

### **11.1 Hypothesis**

Physical Function [AU]

H0: The use of cryotherapy with intermittent dynamic compression has no positive effect on the physical functions of patients after a total knee arthroplasty.

H1: The use of cryotherapy with intermittent dynamic compression has a positive effect on the physical functions of patients after a total knee arthroplasty.

Patient satisfaction [cm]

H0: The use of cryotherapy with intermittent dynamic compression has no positive effect on patient satisfaction of patients after a total knee arthroplasty.

H1: The use of cryotherapy with intermittent dynamic compression has a positive effect on patient satisfaction of patients after a total knee arthroplasty.

Joint circumference [mm]

H0: The joint circumference is not reduced by cryotherapy with intermittent dynamic compression compared to the control group during a hospital stay.

H1: The joint circumference is reduced by cryotherapy with intermittent dynamic compression compared to the control group during a hospital stay.

Skin temperature [C°]

H0: The skin temperature is not reduced by cryotherapy with intermittent dynamic compression compared to the control group during a hospital stay.

H1: The skin temperature is reduced by cryotherapy with intermittent dynamic compression compared to the control group during a hospital stay.

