### 11.4.2 Primary Analysis

The statistical data analysis will be carried out by [name] after completion of the data collection of the entire project.

Repeated measures analysis of variance (MANOVA) 2

factors:

Factor 1: Intervention (Game Ready vs. Control Intervention)

Factor 2: Time (baseline, 4th postoperative day and 6 weeks)

The significance level is set to  $p < 0.05$ . Statistical data analysis is carried out with SPSS.

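### The 0.95 power for 28 subjects in Section 11.2 reproduces only for one outcome's group-by-time interaction with f(V) = 0.8, at an unadjusted 5% level and with no dropout, and the plan states none of these conditions

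*Combined protocol and SAP*

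**What the plan says.** Section 11.2 reports a G*Power calculation in which "a minimum number of 28 subjects was deemed necessary to ensure the statistical power (0.95"), the aim being "to detect a parameter difference at the 5% significance level". The Synopsis (number of subjects) adds "n=28 (14 per group) G-Power analysis: effect size at 0.8". The readable text does not name the effect-size metric, the G*Power test, the outcome or the correlation between time points. Section 11.2 refers to Figure 4 for the calculation. That figure is missing from the copy reviewed and may show some of these.

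The other parts of the plan that bear on the figure are:

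- **Planned test.** Section 11.4.2 specifies "Repeated measures analysis of variance (MANOVA) 2" factors: intervention (two groups) and time (baseline, Day 4, 6 weeks).
- **Endpoint and outcomes.** Section 5.1 makes postoperative Day 4 the primary endpoint. The Synopsis lists ten outcomes, all as primary. The readable text of Section 11.1 states hypotheses for nine of them.
- **Multiplicity.** The Synopsis (statistical considerations) names a "Bonferroni correction" without saying which tests it covers. Section 11.4.2 gives p < 0.05 and does not repeat it.
- **Analysis set.** Section 11.4.1 says "Only complete data sets will be included in the study" and that missing data will not be replaced by new subjects. Section 7.4 says that after a withdrawal the lot goes back into the pot and a new participant is sought. No dropout allowance is stated.

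**The concern.** The power statement carries no conditions, and the effect size of 0.8 carries no unit. Many readers will take 0.8 as a standardised difference between arms and conclude that the trial has 95% power for it on Day 4, on each primary outcome, under whatever correction is applied. Nothing in Section 11.2 tells them otherwise.

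What is at stake is how a null result is read. A trial presented as having 95% power invites the conclusion that a missing difference is evidence of no effect. If the figure belongs to one unadjusted test, a very large multivariate effect and complete data, that conclusion would often be unsafe.

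**Working it through.** **Inputs.** N = 28, 14 per group, effect size 0.8 (Synopsis). Power 0.95, alpha 0.05 (Section 11.2). Two groups and three times (Section 11.4.2).

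**1. Reproducing the plan's figure.** Take the interaction in a repeated-measures MANOVA with 2 groups and 3 times and enter 0.8 as f(V). Then df1 = 2, df2 = N − 3 = 25 and noncentrality λ = f(V)² × N = 0.64 × 28 = 17.92. From the noncentral F at alpha 0.05, power is 0.955 at N = 28 and 0.947 at N = 27. The minimum N for 0.95 is therefore 28, as stated.

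Other ways of entering 0.8 directly, with the total N needed for 0.95:

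| Reading of 0.8 | Total N |
|---|---|
| Two-sample t test, d = 0.8, two-sided | 84 (42 per arm) |
| One-way ANOVA, two groups, f = 0.8 | 24 |
| Univariate repeated-measures between-group effect, f = 0.8, three times, correlation 0 to 0.8 | 10 to 20 |
| Univariate repeated-measures interaction, f = 0.8, three times, correlation 0 to 0.8 | 10 to 4 |
| MANOVA interaction, f(V) = 0.8, two times | 23 |
| MANOVA interaction, f(V) = 0.8, three times | **28** |

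Other models come close to 28 only with a different effect size and an assumed correlation. For example, f = 0.25 at correlation 0.7 gives 28.

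**2. What f(V) = 0.8 means.** For two equal groups λ = (14 × 14 / 28) × D² = 7D², where D is the Mahalanobis distance between the groups on the two time contrasts. So D = √(17.92 / 7) = 1.6.

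The documents give no correlation. Assume the groups differ only on Day 4, by δ SD, with equal variances and equal correlation ρ between times. Then D² = 2δ² / [3(1 − ρ)]. Two results follow:

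- The Day-4 difference implied by D = 1.6 is δ = 1.6 / √(2 / [3(1 − ρ)]).
- The power for δ = 0.8 uses λ = 7 × 2 × 0.64 / [3(1 − ρ)].

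| ρ (assumed) | Day-4 difference implied by f(V) = 0.8 | λ for a 0.8 SD difference | Power of the planned test for 0.8 SD, alpha 0.05 |
|---|---|---|---|
| 0 | 1.96 SD | 2.99 | 29% |
| 0.5 | 1.39 SD | 5.97 | 53% |
| 0.7 | 1.07 SD | 9.96 | 76% |
| 0.8 | 0.88 SD | 14.93 | 91% |

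**3. Bonferroni.** Keep f(V) = 0.8 and N = 28 and replace alpha by 0.05/k. The family size k is an assumption.

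| k | Why this k | Power | N for 0.95 |
|---|---|---|---|
| 1 | Section 11.2 as written | 0.955 | 28 |
| 3 | three pairwise time comparisons | 0.88 | 35 |
| 7 | outcomes measured in both arms at all three times | 0.79 | 40 |
| 9 | hypotheses readable in Section 11.1 | 0.77 | 41 |
| 10 | primary outcomes in the Synopsis | 0.75 | 42 |

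The seven are the KOOS questionnaire, joint circumference, range of motion, skin temperature, pain, the 10-metre walk and the Timed-Up-and-Go. Satisfaction is collected in the Game Ready arm only, and morphine use and length of stay have no baseline value (Sections 5.1 and 9.1).

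**4. Incomplete data.** At f(V) = 0.8 and alpha 0.05, 27 completers give 0.947. An assumed 24 completers give 0.91.

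**The case against.** The strongest reply is that no sum is wrong. The stated inputs, put into the test that Section 11.4.2 plans, return exactly 28 and 0.955. That stands in full.

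A reader might go further and infer that the 0.95 is an arithmetic error and that the real power is 53%, from a two-sided two-sample t test on Day 4 with d = 0.8 and 14 per arm. The documents do not support this. The readable text never calls 0.8 a Cohen's d, and the plan does not use a single-time-point t test. That reading needs 42 per arm, which suggests that the authors did not use it. The 53% in the working above comes from the planned MANOVA at an assumed correlation of 0.5. Its agreement with the t-test figure is no reason to quote it as the trial's power: at 0.8 the same test has 91%.

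A reader might also take 0.75 as the power under the plan's own correction. The Synopsis gives no family, so ten tests is only one possibility. If the correction covers only follow-up comparisons between times, the interaction test for one outcome keeps 0.955.

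Figure 4 may already name the test and the metric, so their absence from the readable text is not held against the plan. Even so, a figure showing f(V) = 0.8 could not turn it into a 0.8 SD difference between arms, and an unadjusted calculation there would leave the mismatch with the Synopsis in place.

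On dropout, Section 7.4 might provide replacements and so restore a margin, but Section 11.4.1 says the opposite.

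**Conclusion.** The concern holds as a matter of unstated conditions, not of faulty arithmetic. The 0.95 is right for one outcome's group-by-time interaction at unadjusted 0.05, with f(V) = 0.8 and 28 complete data sets. Section 11.2 presents it without any of these limits, in a plan with ten primary outcomes, a named Bonferroni correction and a completers-only analysis.

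- For a Day-4-only difference of 0.8 SD, the planned test stays below 95% at every correlation tried from 0 to 0.8, with power between 29% and 91%.
- If Bonferroni applies across tests, power at f(V) = 0.8 is between 0.88 (3 tests) and 0.75 (10 tests).
- The loss of one subject is enough to take even the unadjusted figure below 0.95.

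These results assume that 0.8 was entered as f(V), which is inferred from the match at 28 and should be confirmed against Figure 4. The Day-4 figures also assume equal correlations and a group difference at Day 4 only. The Bonferroni families and the 24 completers are illustrations.

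**What to change.** Keep n = 28 and restate Section 11.2 and the Synopsis so that they:

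1. say that 0.95 applies to one outcome's group-by-time interaction in the planned repeated-measures MANOVA, at unadjusted 0.05, with f(V) = 0.8 and all 28 data sets complete. Check this against Figure 4 first; if the figure shows another test or metric, describe that one and recompute;
2. state which tests the Bonferroni correction covers, and give the power at that corrected level;
3. give the planned test's power for a 0.8 SD Day-4 difference over a stated range of correlations, such as the one tabulated above, labelled as an assumption;
4. state the number of completers assumed, with Sections 7.4 and 11.4.1 reconciled on whether subjects are replaced.

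The 53% from a two-sample t test should not be inserted as the trial's power, because the plan does not use that test.

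The change is to wording only; sample size and procedures stay as they are. The cost is that the stated power becomes less favourable.
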